The main problem is how to detect those tumours that are radiosensitive and will be highly likely to result in CR by CRT only, thus eliminating the need for major surgical resections with

considerable surgical morbidity and impairment of functions, in addition to late postradiation effects.

cCR is currently defined by the four clinical characteristics as described by the Habr-Gama group. At present, it remains unclear whether the additional use of Magnetic Resonance Imaging (MRI) may increase the predictive value of cCR, and conflicting results are reported (18, 19). This may, however, change with future improvements of diagnostic imaging tools and protocols. Further, tissue sampling during observation after CRT has currently no place in enhancing the sensitivity or specificity of cCR (15). Moreover, there are at present no molecular or other tumour characteristics that can predict CR.

According to the Norwegian guidelines – like others – the recommended waiting time before surgery is at least 6 -8 weeks, and up to 10-12 weeks after CRT. A waiting time of 12-13 weeks after long course CRT in tumours that respond is associated with an increased rate of cCR without any impaired prognosis (20). Thus, tumours with a near cCR at 6-8 weeks might result in a cCR at 12-13 weeks, and the patients who do not achieve cCR after 12-13 weeks and then undergo surgery will according to current knowledge not have inferior prognosis compared to those operated at 6 -8 weeks.

There are only a few studies in the literature that report on more than 50 – 100 patients in single centre series (21, 22). Due to the nature of the disease and treatment, such studies are not easy to conduct. Furthermore, the inclusion and exclusion criteria used in the various studies differ considerably, and the study populations are heterogeneous. The protocols vary with regard to the use of CRT and the waiting time for assessment of the response. Therefore, studies based on population based registries, such as the Cancer Registry of Norway or the Norwegian Colorectal Cancer Registry, are highly likely to provide important information.

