The W&W has gained great interest, as it provides the possibility to cure the patients without the need of major surgery and its consequences on functional outcomes and lifelong morbidity, and thus preventing overtreatment. However, this treatment concept is currently regarded as experimental and has not yet become part of commonly accepted guidelines. There is a need to increase the knowledge on the concept of cCR and CR in a population based patient cohort with a standardized treatment algorithm and follow-up.

Aim of the study

The aim of this study is to estimate the rate of regrowth among patients with locally advanced rectal cancer treated with neoadjuvant treatment with radiotherapy or chemoradiotherapy, where complete clinical response has been obtained, and thus to determine the positive predictive value of cCR in a national cohort.

Objectives and endpoints

Primary endpoint is the *rate of regrowth* among patients with cCR who follow the W&W protocol after preoperative radiotherapy or chemo-radiotherapy, in order to determine the positive predictive value of cCR.

Secondary endpoints are

- The rate of cCR after preoperative CRT
- To calculate the diagnostic accuracy of the clinical diagnosis of complete response
- The rate of metachronous distant metastases in patients following the W&W protocol
- The rate of metachronous metastasis and recurrence rate after ypCR
- Overall and cancer-specific survival of patients with cCR following the W&W protocol compared to patients with ypCR, i.e. patients with complete pathologic response after resection.
- Assess the rate of patients who otherwise would have had an APR
- Patient-reported outcome measures, such as Low anterior resection syndrome (LARS) and quality of life (QoL)
- To calculate the costs of treatment for W&W after cCR as compared to surgical treatment
- To assess the diagnostic accuracy of MRI in the diagnosis of complete response

Design

The current study is designed as an open prospective population-based study. All patients diagnosed and treated with radiotherapy or chemo-radiotherapy for rectal cancer in Norway will be eligible for this study, provided signed informed consent given before inclusion.

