- **Complete clinical response** at 6-8 weeks after neoadjuvant treatment includes two *negative signs*, i.e., the disappearing of the visible tumour leaving a flattening of the mucosa on the inner bowel wall, no tumour is seen, and the disappearing of any ulcer. These signs are *mandatory*. Two other criteria include *positive signs*, i.e., whitening of the previous tumour site appearing almost as a small white spot to merely a great area, and development of telangiectasia. These positive signs depend to a higher degree on time and individual interpretation, and are *not mandatory*:
 1. Flattening of the tumour site (mandatory)
 2. No ulcer visible (mandatory)
 3. Whitening of the tumour site (not mandatory)
 4. Visible telangiectasia (not mandatory)
- **Near Clinical Complete Response (near-cCR)** is defined as a nearly complete disappearance of the tumour and/or the ulcer of more than 75% at 6-8 weeks post RCT as determined by the clinician. A near-cCR may result in cCR after 11-12 weeks post CRT, and in this case the patient will be eligible for inclusion into the W&W

protocol at that time. Otherwise, the condition is not a cCR and surgery is offered immediately.

Patients with cCR after preoperative CRT who decline the W&W protocol and wish to undergo surgery, or patients with near, but not complete clinical response will be asked to give consent to participate for registration in the database as controls.

Exclusion Criteria

- Patients without cCR
- Patients unable to give informed consent
- Patients with short course radiotherapy (5x5 Gy) without additional chemotherapy, or patients receiving less than 40 Gy in long course CRT
- Patients with cCR but with increasing tumour growth on MRI after preoperative treatment
- Patients with metastatic disease at the time of diagnosis with the exception of those who are eligible for "liver first" treatment approach as part of an intention to cure approach.
- Patients previously diagnosed and treated for malignant disease in the pelvic region with radio- or chemoradiotherapy
- Other circumstances that may interfere with successful participation in the W&W protocol

Radiation and chemoradiation

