Neoadjuvant treatment will be given based on a decision by the MDT and according to national guidelines that apply at any given time during the study period. Preoperative radiotherapy is currently given as long course radiotherapy to 50 Gy with concomitant chemotherapy (capecitabine or 5-fluorouracil). Patients treated with short-course 5x5 Gy with combination chemotherapy are also eligible for participation. Neoadjuvant treatment with any modifications due to patient-related factors are acceptable as far as the effect of received treatment is considered to be at least 80% of standard treatment.

Response evaluation before enrolment in the study

All patients who receive preoperative CRT will be evaluated for treatment response at approximately 6 weeks after the last radiation treatment by MRI and clinical examination, including digital rectal examination (DRE) and rigid proctoscopy.

Patients with cCR (i.e., ycT0N0) will be invited for participation in the study.

Patients with near-cCR will be invited to undergo a second evaluation for cCR at 12 weeks for participation in the study. State of clinical tumour regress will be documented by endoscopic photography imaging when cCR is concluded. Patients with initial near-cCR, but without cCR at 12 weeks will be advised to undergo surgery according to current guidelines. The accuracy of DRE in cCR is not evident. When either DRE and/or MRI suggest a tumour in patients who otherwise fulfil cCR criteria, they are offered surgery and asked for inclusion into the study without W&W protocol.

Patients who fulfil the criteria for cCR as defined at 6 weeks or 12 weeks will be asked for participation in the W&W protocol. All other patients who were considered for cCR without a final diagnosis of cCR will not be eligible for the W&W protocol, but they will be asked to participate in the study by recording their data of treatments and outcomes in order to calculate the necessary statistics (e.g., sensitivity, specificity or likelihood ratios of possible prognostic or predictive factors for the study endpoints). These patients will be offered systematic follow-up as described in national guidelines.

Treatment course of the included patients and follow-up

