Patients eligible for the present study will be recruited from all patients undergoing neo-adjuvant treatment for rectal cancer within 15 cm distance from the anal verge according to national guidelines. Treatment decisions will be made at multidisciplinary team meetings according to national guidelines, and after information and discussion with the individual patient based on individual informed consent.

Evaluation after neo-adjuvant treatment and eventual inclusion into the cCR protocol will be done after 6 weeks based on clinical and radiological examinations as indicated in the flow chart below. Blood tests at inclusion include analysis of CEA, B-RAF and K-RAS biomarkers.

In case of persistently elevated or increasing serum CEA levels, the presence of synchronous distant metastases has to be ruled out, and the conclusion of cCR has to be thoroughly reconsidered.

Radiological response evaluation

Multiparametric MRI for estimating tumour response and tumour regrowth after CRT is a developing diagnostic tool and consists of many different techniques. In this population-based multicentre study, the MRI protocol needs to be standardized and based on the best-explored and most robust MRI parameters; T2W and diffusion weighted imaging (DWI). The two most promising parameters for estimating cCR are tumour volume reduction, measured at T2W, and loss of tumour signal assessed at both T2 and DWI. Volume reduction has a high sensitivity for prediction of cCR (19) and will be assessed by the *MR Tumour*

Regression Grade (mrTRG), appendix I. Maas *et al* have shown that disappearance of tumour signal at T2W and DWI indicated cCR and furthermore that the diagnostic performance improved if MRI and clinical assessment were combined (15). A five-point confidence level scale (appendix II) will be used to record the tumour signal disappearance at T2&DWI. T2&DWI is also promising for early detection of regrowth in a *watch and wait* (W&W) program (24) and will also be recorded using a five-point confidence level scale, see appendix I.

Minimum required sequences in the MRI examination are:

[figure not shown]
- Transversal, sagittal and coronal 2D T2W *or* an isotropic 3D T2W
- Hi-resolution T2W TSE perpendicular to the tumour/bowel wall interface
- Transversal DWI with at least two b-factors 0 -1000

[figure not shown]
To reduce susceptibility artefacts from bowel air, a rectal enema should be administered prior to the MRI examination.

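### Clinical and MRI accuracy are separate endpoints, but the planned table measures only the combined call and no stated reading order keeps the two verdicts independent

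*Protocol*

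**What the plan says.** Objectives and endpoints lists the diagnostic accuracy of the clinical diagnosis of complete response and, as a separate item, "To assess the diagnostic accuracy of MRI in the diagnosis of complete response". Background gives the reason for interest: "it remains unclear whether the additional use of Magnetic Resonance Imaging (MRI) may increase the predictive value of cCR".

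The definition of cCR varies by section. Background and the W&W inclusion criteria define it by four luminal signs, two of them mandatory, with no MRI element. Response evaluation before enrolment has patients "evaluated for treatment response at approximately 6 weeks after the last radiation treatment by MRI and clinical examination", equates cCR with a T and N category ("Patients with cCR (i.e., ycT0N0) will be invited for participation in the study"), and lets imaging override the luminal signs: "When either DRE and/or MRI suggest a tumour in patients who otherwise fulfil cCR criteria, they are offered surgery". Treatment course of the included patients and follow-up makes inclusion "based on clinical and radiological examinations as indicated in the flow chart below". Exclusion Criteria adds: "Patients with cCR but with increasing tumour growth on MRI after preoperative treatment".

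MRI is scored on its own scales. Radiological response evaluation names mrTRG and states: "A five-point confidence level scale (appendix II) will be used to record the tumour signal disappearance". The scales themselves are printed in Appendix I.

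The 2x2 table under Study population and sample size has one index test, W&W (cCR) against no W&W (no cCR), with cells 85, 30, 15 and 870.

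**The concern.** Two accuracy endpoints call for two test results, each obtained without knowledge of the other. Here MRI is both a test under evaluation and a component of the diagnosis that forms the rows of the table. That is incorporation: a row labelled as the clinical diagnosis already contains the MRI result.

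The text shown also gives no reading order, no masking and no requirement to write down the luminal/DRE verdict before the MRI is known, or the reverse. A surgeon who has seen a suspicious scan may grade the mucosa differently, and a radiologist who knows the endoscopy finding may score differently. The two would then agree more than they would on their own, and no later analysis can restore the independence.

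At stake are two secondary endpoints and the question that Background leaves open, namely whether MRI adds to luminal cCR. The primary endpoint, regrowth among W&W patients, is not touched.

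**Working it through.** **1. Reproduce the planned table.** Inputs are the four cells under Study population and sample size. A positive test means called cCR.

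- Margins: 85 + 30 = 115; 15 + 870 = 885; 85 + 15 = 100; 30 + 870 = 900; total 1000. These agree with the print.
- Sensitivity 85/100 = 85.0%; specificity 870/900 = 96.7%.
- PPV 85/115 = 73.9%; NPV 870/885 = 98.3%.

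The text above the table has 100 W&W patients with up to 30 regrowths (PPV 70%) where the table has a row of 115. That mismatch is a separate matter and does not affect the argument.

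**2. What these figures describe.** Let E be luminal/DRE complete and M be MRI complete. Assume a patient is called cCR only when both hold, which is how the override sentence reads. Then:

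- P(E and M | true CR) = 0.85. This cannot exceed P(E | true CR) or P(M | true CR), so each component's sensitivity is between 85% and 100%.
- P(E and M | no CR) = 30/900. Each component's false-positive rate is at least this, so each component's specificity is between 0% and 96.7%.

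The table allows nothing narrower.

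**3. Illustration.** The splits below are assumptions, not protocol figures. Each divides the 15 missed complete responses and the 870 correctly refused patients by which test refused them.

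| | Split A | Split B |
|---|---|---|
| 15 missed: E only / M only / both | 10 / 3 / 2 | 3 / 10 / 2 |
| 870 refused: E only / M only / both | 30 / 10 / 830 | 20 / 60 / 790 |
| Sensitivity, E alone | 88/100 = 88.0% | 95/100 = 95.0% |
| Specificity, E alone | 860/900 = 95.6% | 810/900 = 90.0% |
| PPV, E alone | 88/128 = 68.8% | 95/185 = 51.4% |
| Sensitivity, M alone | 95/100 = 95.0% | 88/100 = 88.0% |
| Specificity, M alone | 840/900 = 93.3% | 850/900 = 94.4% |
| False positives of E removed by MRI | 40 - 30 = 10 | 90 - 30 = 60 |
| Resulting table | 85/30/15/870 | 85/30/15/870 |

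MRI contributes little in A and much in B, yet the planned table is the same.

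**4. What else the MRI result decides.** Among patients with luminal cCR, a suspicious MRI leads to an offer of surgery, and those who accept are verified by specimen. A clear MRI opens W&W, where verification is by regrowth during follow-up. The MRI result therefore also selects the reference standard. Endoscopic photographs are required only once cCR has been concluded, so a patient refused because of MRI need not have an image for a later independent luminal reading.

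**The case against.** The strongest reply is that the raw material for a separate analysis is largely planned. The luminal signs are itemised and MRI has its own ordinal scales. Patients with luminal cCR and a suspicious DRE or MRI are asked to join without W&W, patients refused cCR are registered expressly for accuracy statistics, and cCR patients who decline W&W are registered as controls. A cross-table of luminal verdict by MRI score is thus possible, and its layout can be left to the SAP, which is not shown. The flow chart is also not shown and might give an order of examinations. The added value of MRI is a background question, not a listed endpoint.

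Much of this stands. It rules out three stronger readings that a reader might infer:

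- *MRI is negative in every W&W patient, so its sensitivity for residual tumour there is 0/30 and its specificity 85/85.* The protocol fixes no cut-off for when MRI suggests a tumour, and the middle level of the five-point scale leaves both possibilities open. Those fractions rest on a binary cut-off that the documents do not give. Baseline MRI probably varies little among W&W patients, but ordinal variation may remain.
- *Only W&W patients are verified.* Operated patients have a specimen, and registered patients outside W&W are offered systematic follow-up.
- *The added value of MRI is unrecoverable.* Part of it can be recovered from the cross-table.

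The reply does not reach the reading order. That is trial conduct, which the SAP cannot supply afterwards, and the cross-table is only as good as the independence of its two margins.

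**Conclusion.** The concern holds in a limited form. The planned table estimates the accuracy of the combined clinical-plus-MRI rule, 85.0% sensitivity and 96.7% specificity as planned. For each component it gives only a floor of 85% for sensitivity and a ceiling of 96.7% for specificity. These bounds assume that cCR is called only when all tests are negative. The size of any review bias cannot be derived from the document. That no separation of the readings exists is a statement about the text shown and excludes the flow chart.

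Separate signing would remedy review bias and the mislabelled index test. It would not remove the MRI gate or the difference in reference standard, so even afterwards the added value of MRI is an estimate with a stated limitation and cannot be read off directly. The point is worth acting on because the change is cheap and the information cannot be recreated later. It concerns secondary endpoints only.

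**What to change.** In Response evaluation before enrolment and Radiological response evaluation, fix the order of recording at the 6- and 12-week evaluations:

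1. The luminal/DRE verdict is signed before the MRI result is seen.
2. mrTRG and the five-point score are signed before the endoscopy/DRE result is seen, with a note of whether the radiologist judged that the scan suggested a tumour.
3. The combined decision is recorded last. Who is offered surgery or W&W stays as it is.

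Under Organization, patients are referred to a university hospital only after the 6-week evaluation has raised possible cCR, so steps 1 and 2 must also be done at the first hospital before referral.

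Report three tests: luminal/DRE alone, MRI alone and combined. Show luminal-cCR/MRI-positive and luminal-cCR/MRI-negative patients in separate rows, and state that the first are verified mainly by specimen and the second mainly by regrowth follow-up. Label the existing table as the combined call. The sections that define cCR by luminal signs alone and those that include MRI must be reconciled.

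Cost: signed fields in a fixed order, one of them extra at referring hospitals, and slightly less convenient reporting, since each reader works without the other's result until signing. No additional reader, scan or procedure is needed.

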For a more detailed MRI protocol see appendix II.

Follow-up of the patients in the W&W protocol will be done according to the schedule outlined below, and up to 8 years, as some recurrences or regrowths may occur later than within the 5 year period commonly used for follow-up of patients with rectal cancer.

Flow chart of W&W protocol

Schedule for W&W protocol:

Clinical evaluation

- Every second month 1. year
- Every third month 2. year
- Every sixth month 3. year
- Thereafter routine systematic follow-up according to national guidelines extended up to 8 years

MRI evaluation

- Every second clinical evaluation the 1. and 2. year, then every sixth month

Serum-CEA measurement

- At all clinical examinations

Systematic follow-up for distant metastases according to national guidelines for systematic follow-up extended to 8 years

Analysis of biological material

In addition to clinical outcomes, it will be of great interest to analyse available biological material with regard to biological markers that may indicate a clinical response, or a regrowth. This is particularly important for the current study as a national multicentre study. For this purpose, it will be of great interest to perform molecular-biological analyses of tissue specimens obtained from diagnostic procedures and surgical specimens after resection. This will be limited to tissue obtained in routine diagnosis, and when patient consent is given.

Patient-reported outcomes

PROMs will be assessed with the LARS score (see Appendix III), and the QLQ-C30 and QLQ-CR29 scores. EORTC-QoL C30 and C29 are generally accepted tools for measuring the quality of life of patients with colorectal cancer. According to the user agreement as defined by the EORTC group, the scores are not displayed in the protocol.

Patients will complete these questionnaires at the time of inclusion, and thereafter at 1, 3 and 5 years follow-up.

Withdrawal from the study

Patients enrolled in the W&W protocol can withdraw from the study at any moment without giving any reason. Data that have been registered as part of the study will not be deleted, unless the patient requests this specifically. Data that are part of mandatory public registration to the Cancer Registry of Norway will be recorded consecutively according to national legislation.

Adverse events

Adverse events (AE) are defined according to the Common Terminology Criteria for Adverse Events (CTCAE), version 4.0 (published: May 28, 2009 v4.03: June 14, 2010).

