Estimation of sample size is based on the aim of this study to detect the sensitivity (i.e., true positives) and specificity (i.e., true negatives), as well as 1-sensitivity (false positives) and 1-specificity (i.e., false negatives) in order to characterize the ability to correctly diagnose patients with cCR with a minimum of regrowth (i.e., false negatives) or unnecessary resections (i.e., false positives). Based on these estimations, it will be possible to achieve the primary endpoint of the study, i.e. the rate of regrowth, and to calculate positive predictive value of the diagnosis of cCR among patients who follow the W&W protocol after preoperative chemoradiotherapy.

As the present study is a prospective observational study, and not a clinical trial that aims to prove the superiority or non-inferiority of a specified treatment, power calculations that result in *numbers needed to treat or to harm*, do not apply here for the estimation of number of patients to include.

By including patients into the study who wish to undergo surgical resection despite the clinical finding of cCR, and decide not to follow the W&W algorithm, it will be possible to calculate these parameters based on a 2x2 table on the following assumptions based on results from current literature:

- During this time period, a tenfold/approx. 1000 patients will receive neo-adjuvant treatment
- Of those, 100 patients with cCR to enter the W&W protocol
- Of those 100, it may be assumed that
 - 85 will have a true CR
 - 15 will have ypCR (i.e., ypT0) after surgical resection
 - of those 100 patients, up to 30 may have regrowth after initial cCR within the W&W protocol
- Finally, 900 of 1000 (i.e., 870 patients + 30 patients with regrowth) will have ypT1-4 after surgical resection

Accordingly, the study aims to include at least 100 patients with cCR who choose to follow the W&W algorithm.

	True CR	No CR	
W&W (cCR)	True positive N=85	False positive N=30 (regrowth)	115
No W&W (No cCR)	False Negative N=15	True Negative N=870	885
	100	900	1000

Based on these figures, it will be possible to calculate sensitivity, specificity, 1-sensitivity, 1-specificity, positive and negative predictive values, positive and negative likelihood ratios, and perform ROC curve analysis.

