The study will include patients until a number of 100 patients has been entered the W&W protocol. Taking into account that 70% of all eligible patients with cCR patients will be identified, i.e. annually 31/50 will be included nationwide, an inclusion period of at least three years will be needed to achieve the goal of 100 study participants. Taking into account that some patients will reject participation in the study and/or decide to withdraw, or be lost to follow-up by other reasons, an inclusion period of up to 5 years might be necessary to achieve the inclusion goal.

One year after start of inclusion, the steering group will evaluate the recruitment with regard to the feasibility of the inclusion goal.

Data collection

Data collection will include clinically relevant variables that are part of common clinical practice independently of the cCR protocol, and that are part of the mandatory public registries (i.e., CRN and NCCR), such as:

- Patient characteristics
- Tumour characteristics (clinical, imaging, pathological and biological), values of blood tests
- Data on oncological treatment (radiation, chemotherapy)
- Surgical procedures
- Pathology reports
- Follow-up data, including possible regrowth, recurrence and metastases, and survival
- PROMs

Data will be collected and recorded at every patient visit and assessment. Given the limited number of patients, data will be collected on paper sheets temporarily at every participating study site under secure circumstances. After one year of inclusion a first interim analysis of all cases will be performed, and data entered into a suitable database provided by the NCCR.

Coupling with other national databases

To enhance data quality, or to increase the information available in the dataset, it will be useful to couple the current dataset with other national registries:

- Norwegian Patient Registry
- Cancer Registry of Norway
- Norwegian Colorectal Cancer Registry
- Norwegian Quality Registry for Gastro-intestinal Surgery (NoRGast)
- The Norwegian Prescription Database

The patients will be asked to consent to coupling to those registries. The study protocol requires the possibility to use indirectly identifiable data due to the coupling of databases.

Statistics

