For analysis of the study, standard descriptive and analytic statistics will be applied when appropriate, and according to the distribution of the various variables. Multivariable analyses will be performed when appropriate with regard to relevant outcome variables, and in order to detect independent predictors of the outcome in question.

Survival analyses will be performed by Kaplan-Meier estimates and factors compared by using the log rank test. Multivariable analysis for time-dependent outcomes will be performed by Cox proportional Hazards analysis in order to detect independent predictors of the outcome in question.

The steering group has the necessary statistical knowledge and competency to provide appropriate statistic evaluation and analysis.

Organization

Patients with rectal cancer will be treated at all Norwegian hospitals that offer diagnosis and treatment for rectal cancer within the public specialist health service and according to national regulations and guidelines. When evaluation at 6 weeks after completed radiation indicates a possible full or near cCR, the patient will be referred to the cooperating University Hospital for further evaluation and recruitment to the W&W protocol when indicated, and informed consent will be obtained.

At each University Hospital, two dedicated colorectal surgeons will examine these patients, include in the W&W protocol and perform follow-up as described according to commonly agreed definitions. They will maintain the data entry forms and registration at the national registries.

In the case of equivocal or uncertain findings, these will be discussed in a collegial forum to achieve consent and decisions.

The W&W protocol will be referred to in the national guidelines as an ongoing study, and thus represent a treatment within a scientific study protocol. The study will be registered on public Norwegian websites such as <https://kliniskestudier.helsenorge.no>, and will be registered at clinicaltrials.gov.

Costs, finances and resources

The W&W protocol will be performed within the public specialist health care. Examinations that are part of the W&W protocol are mostly inexpensive clinical examinations or routine blood tests, with the exception of MRI examinations. However, the number of study participants is low, and as included patients will not need hospital consumptions related to surgery, the total economic load of the study is considered to be low.

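### The primary endpoint (regrowth rate and positive predictive value of cCR) has no time point and is tied to a two-outcome 2x2 count that cannot handle incomplete follow-up

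*Protocol*

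**What the plan says.** The Protocol defines the endpoint under Objectives and endpoints: "Primary endpoint is the *rate of regrowth* among patients with cCR who follow the W&W protocol after preoperative radiotherapy or chemo-radiotherapy". The stated purpose is to determine the positive predictive value (PPV) of cCR. No time origin, time point or rule for incomplete follow-up is attached.

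The route to the endpoint is under Study population and sample size. The aim there is to estimate sensitivity, specificity and their complements, and then: "Based on these estimations, it will be possible to achieve the primary endpoint of the study, i.e. the rate of regrowth". The protocol adds that "it will be possible to calculate these parameters based on a 2x2 table". In that table every watch-and-wait patient is either a true CR or a regrowth.

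Other sections describe incomplete and staggered observation:

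- Follow-up runs "up to 8 years, as some recurrences or regrowths may occur later than within the 5 year period" (text before the follow-up schedule).
- Time schedule gives an inclusion period of three to five years and 8 years of follow-up per patient.
- The sample-size section expects that "some patients will reject participation in the study and/or decide to withdraw, or be lost to follow-up by other reasons", and answers with a longer inclusion period.
- Data collection plans a first interim analysis after one year of inclusion.

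The Statistics section says "Survival analyses will be performed by Kaplan-Meier estimates and factors compared by using the log rank test", and gives Cox models for time-dependent outcomes. Neither method is linked to regrowth.

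**The concern.** In a patient who is not resected, a true complete response can only mean no regrowth up to some time. Without that time, the PPV and the other accuracy measures have no defined reference standard. A two-cell count also needs each patient's final status, which the protocol expects not to have for everyone.

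The reported figure would then depend on the date of the data cut and on how incompletely followed patients are classed, as well as on the disease. At stake is the study's headline result. A regrowth rate that is too low makes omitting surgery look safer than it is, and one that is too high does the reverse.

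**Working it through.** **The plan's own figures.** The text assumes 100 watch-and-wait patients, of whom "of those 100 patients, up to 30 may have regrowth after initial cCR within the W&W protocol", a rate of 30/100 = 30.0% (Wilson 95% CI 21.9-39.6%). It also says of the same 100 that "85 will have a true CR". But 85 + 30 = 115, which is the table's row total, so the table gives 30/115 = 26.1% regrowth and PPV 85/115 = 73.9%. The 100 and the 115 do not agree. That is a separate matter to reconcile; 30% is used below.

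**Inputs from the protocol.** True regrowth F = 30%, taken here as the 8-year value; accrual of 3 or 5 years; follow-up capped at 8 years.

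**Assumed inputs, because the protocol gives none.** Uniform accrual. Exponential time to regrowth, with a timing parameter s of 0.60 to 0.90 (roughly the share of regrowths seen by 2 years), scaled to reach F at 8 years. Yearly loss and death of 0/0, 3/2, 5/3 or 10/3 per cent, independent of regrowth.

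**Formula.** Let λ = -ln(1 - s)/2 and c = -ln(1 - loss) - ln(1 - death). For a patient with potential follow-up u, the chance of an observed regrowth is

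F × [λ / (1 - e^(-8λ))] × [1 - e^(-(λ+c)u)] / (λ + c).

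Averaging over u gives the expected crude proportion, that is, regrowths seen divided by all entered.

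**Worked case at the end of accrual** (s = 0.80, 3-year accrual, no loss or death): λ = 0.805. The average of 1 - e^(-λu) for u from 0 to 3 is 1 - (1 - e^(-2.414))/2.414 = 0.623. Then 30% × 0.623/0.998 = 18.7%.

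**Worked case after 8 years for all** (s = 0.80, loss 5%, death 3%): c = 0.0818 and λ + c = 0.886. Then 30% × (0.805/0.886) × (0.999/0.998) = 27.3%.

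**Range of the crude count over all entered, against a true 30%:**

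| Data cut | Lowest | Highest |
|---|---|---|
| One year after start | 5.8% | 12.2% |
| End of accrual | 12.7% | 24.8% |
| Two years after end of accrual | 20.4% | 29.5% |
| 8 years for everyone | 23.5% | 30.0% |

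The last row reaches 30.0% only with no loss and no death.

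**How much of the 8-year shortfall is due to death.** In the lowest case (s = 0.60, loss 10%, death 3%), setting loss to zero and keeping death gives c = 0.0305 and 30% × (0.458/0.489) × (0.980/0.974) = 28.3%. That is the cumulative incidence with death as a competing event. So of the 30.0 - 23.5 = 6.5 points, about 1.7 come from death and are not an error in a cumulative incidence. The other 4.8 (28.3 - 23.5) come from treating lost patients as free of regrowth.

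**Exclusion instead.** Suppose patients lost or dead without regrowth are dropped (s = 0.80, loss 5%, death 3%, 8 years). Observed regrowths are 27.3 per 100. Patients completing 8 years without regrowth are 70 × (0.95 × 0.97)^8 = 36.4 per 100. The rate becomes 27.3/(27.3 + 36.4) = 43%.

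**The case against.** The table holds projected counts in a sample-size section and is not written as an analysis rule. A reader might infer from it that patients with short follow-up, withdrawal, loss or death are to be counted as true complete responses, so that regrowth is necessarily understated. The protocol does not support that reading. No section says how such patients are classed. Longer inclusion as the answer to refusal and loss could mean replacement or exclusion, and exclusion moves the bias the other way. Death does not belong in that charge either: a cumulative incidence also leaves deaths without regrowth among the non-regrowths.

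The end-of-accrual figures describe a cut that the protocol does not schedule. If the analysis waits until everyone has had 8 years, staggered entry drops out and only loss and death matter. Loss may also be small: visits are frequent in the first years, registered data are kept after withdrawal unless the patient asks for deletion, mandatory Cancer Registry recording continues, and registry linkage by consent is planned. The general wording on Kaplan-Meier and Cox could cover regrowth, and estimator details are often left to a statistical analysis plan.

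These points settle the wording and the size. They do not remove the defect. The time point of a primary endpoint is part of its definition, 8 years is stated as a length of follow-up and not as the time at which a true complete response is judged, and the only method that the protocol attaches to this endpoint is the two-outcome table.

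**Conclusion.** The concern holds in this form: the primary endpoint has no time point, and the method tied to it cannot accommodate the staggered entry, withdrawal, loss and late regrowth that the protocol itself expects. The direction of error is not fixed. For a true 30%, a count over all entered is about 13-25% at the end of accrual and 24-30% after 8 years for everyone, while exclusion gives about 43% in the scenario shown. The possible shift therefore runs from nothing to some 17 points down or 13 points up, against a sampling interval of roughly 22-40% for 30 regrowths in 100.

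Only the 30%, the accrual period and the 8 years come from the protocol. Timing, loss and death are assumptions, and lower loss or faster regrowth narrows the range.

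**What to change.** - **Endpoint.** Define it as the cumulative incidence of regrowth at a fixed time from the date cCR was declared. That origin suits both patients with cCR at the first evaluation and those who reach it at the second. Two years is one possible horizon, with later times up to 8 years as supporting results. A 2-year figure must be labelled as such: under the assumptions above it would be 18.5-27.0% (30% × s/(1 - e^(-8λ)) for s = 0.60 and 0.90) when the 8-year value is 30%.
- **Estimator.** Use the Aalen-Johansen estimator, with loss and withdrawal censored and death without regrowth as a competing event.
- **PPV.** Report 1 - CIF(t) with a 95% CI as the regrowth-based PPV at that horizon. State that deaths without regrowth count as non-regrowth in it.
- **2x2 table.** Fill the watch-and-wait row from this estimate (number entered × CIF(t) and number entered × [1 - CIF(t)]), not from raw counts.
- **Timing.** Do the primary analysis when the last watch-and-wait patient reaches the horizon.

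The cost is a change of wording and standard software. The existing schedule covers the visits. The one drawback is that the primary report waits until the last patient reaches the horizon.
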